STUDY POPULATION: Two hundred treatment-seeking individuals with Diagnostic and Statistical Manual of Mental Disorders Fourth Edition (DSM-IV) criteria for methamphetamine dependence determined by Mini International Neuropsychiatric Interview (MINI) DSM-IV version will be randomized to receive either bupropion or placebo. Only those subjects who report 29 or less days of methamphetamine use in the 30 days prior to signing consent will be considered for enrollment. Males and females, 18 to 65 years-of-age, inclusive, with at least one methamphetamine-positive urine specimen provided during the screening or baseline period prior to randomization (or provide collateral information to verify recent use if a positive urine sample can not be obtained), who verbalize the ability to understand and provide written informed consent, will be included.

INTERVENTIONS: Subjects randomized to the bupropion group will receive 150 mg of sustained-release (SR) bupropion once daily for 3 days then twice daily, i.e., a total of 300 mg/day, for a total of 12 weeks (dose taper will be performed the last 3 days of the 12 weeks, to 150 mg per day). Subjects randomized to the placebo group will receive matched placebo tablets according to the same schedule. All subjects will receive two 60 minute early recovery group

sessions after signing consent but before randomization, and manual-guided group cognitive behavioral therapy (CBT) consisting of three 90 minute sessions/week during the 12 weeks of study interventions and once weekly during the 4 weeks of follow-up.

SAFETY ASSESSMENTS: All subjects enrolled in the study will have a physical examination, a 12-lead electrocardiogram (ECG), and clinical laboratory studies (blood chemistry, hematology, Hepatitis B and C virus serology, syphilis test, tuberculin test, and urinalysis) performed during screening. If the potential participant is female, a pregnancy test will also be performed during screening, on the first day of investigational product administration, at Study Weeks 4, 8, and 12 or earlier termination. Vital signs, concomitant medication use, and a urine screen for other substances of abuse will be assessed weekly during the study. Adverse events (AEs) will be assessed at each visit. At the end of the study, or if terminated early, subjects will be evaluated for AEs, vital signs, physical examination, clinical laboratory studies, and ECG.

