4.2.3 Bupropion Pharmacology

Pharmacokinetics. Tablets of bupropion hydrochloride come in immediate- and SR formulations. The bupropion SR, 150 mg, twice daily formulation will be used for this study. Bupropion SR has been shown to be bioequivalent to 100 mg three times daily of the immediate release formulation with regards to rate and extent of absorption and parent drug and metabolites in clinical trials for depression. Better compliance is expected with twice daily dosing as opposed to thrice daily dosing making bupropion SR an obvious choice for study.

The half-life of bupropion is approximately 21 hours after chronic dosing. Peak plasma concentrations of bupropion are achieved within 3 hours following oral administration. The mean peak concentration (C_{max}) values were 91 and 143 ng/mL from 2 single-dose (150-mg) studies. At steady state, the mean C_{max} following a 150-mg dose every 12 hours is 136 ng/mL. In a single-dose study, food increased the C_{max} of bupropion by 11% and the extent of absorption as defined by area under the plasma concentration-time curve (AUC) by 17%. The mean time to peak concentration (T_{max}) was prolonged by 1 hour. This effect was of no clinical significance. Steady state plasma concentrations of bupropion are reached within 8 days. Four basic metabolites have been identified. These metabolites are pharmacologically active, but their potency and toxicity relative to bupropion have not been totally characterized. They may be of clinical importance because the plasma concentration of metabolites is higher than those of bupropion.

Bupropion is a racemic mixture. The pharmacologic activity and pharmacokinetics of the individual enantiomers have not been studied. Bupropion follows biphasic pharmacokinetics best described by a 2-compartment model. The terminal phase has a mean half-life (\pm % CV) of about 21 hours (\pm 20%), while the distribution phase has a mean 57 half-life of 3 to 4 hours.

In vitro tests show that bupropion is 84% bound to human plasma proteins at concentrations up to 200 μ g/mL. The extent of protein binding of the hydroxybupropion metabolite is similar to that for bupropion, whereas the extent of protein binding of the threohydrobupropion metabolite is about half that seen with bupropion. The volume of distribution (V_{ss}/F) estimated from a single 150-mg dose given to 17 subjects is 1,950 L (20% CV).

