11 INTERVENTIONS

11.1 Investigational Products

Subjects assigned to receive bupropion hydrochloride SR will receive 150 mg every day for the first 3 days of dosing which will be increased to 300 mg daily (one tablet twice a day) for the duration of dosing period until the final dose taper. The dose will be tapered to 150 mg every day for 3 days until termination or the last scheduled day of the 12-week intervention period. Subjects will be informed that they must taper the dose for three days before stopping the investigational products completely in the event that they decide to terminate from the study prematurely. Subjects assigned to the placebo group will receive matched placebo on the same schedule as the bupropion group. Subjects will be instructed to take investigational products at least 8 hours apart when taking investigational products twice daily and not to take two tablets at once if a dose is missed. During the last 3 days of study interventions during Week 12 or before termination, subjects' investigational products will be tapered down to 150 mg (or equivalent placebo) each day by taking only one tablet per day.

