^a The family history questionnaire will only be done on subjects who consent to the genetics testing even if they are considered a screen failure for the bupropion/methamphetamine study.

^b An alcohol breathalyzer test will be performed in accordance with institutional policy and state law.

^c The pregnancy test on Day 1 must be performed prior to randomization and administration of the first dose of investigational product.

^d These assessments are performed after the first screening visit

^e Eligibility is checked during screening and at baseline visits as data become available such that if a subject does not meet inclusion or exclusion criteria, the subject is no longer screened.

^f The ASI-Lite will be performed during screening; however, if the entire screening/baseline period takes longer than 14 days, the ASI must be repeated such that the it is collected during baseline.

^g Assay for methamphetamine and creatinine as well as the urine toxicology screen will be performed only for urine samples collected from the subjects who are randomized into the study.

^h Blood for RNA analysis should be collected at the same time of day at every collection time point to control for circadian rhythm effects on expression. One RNA tube will be collected during screening/baseline and at all other time points during the intervention phase of the study.

ⁱ During the intervention phase, blood for bupropion levels will be taken before the daily dose.

^j Investigational product compliance is reviewed at every clinic visit with the subject by self report but the pill count is only done weekly.

^k Two 60 minute early recovery skills group sessions given weekly until randomization occurs. Compliance should be checked at each visit and verified with the CBT attendance log.

¹ These assessments are performed at the last visit of Week 12 or at earlier termination.

^mCBT sessions are performed once a week during the follow-up period.

ⁿ Bupropion/hydroxybupropion will be analyzed after study closure only in those assigned to a bupropion treatment group as a surrogate marker for medication compliance.

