13.3 ASSESSMENTS DURING THE INTERVENTION PHASE

Over the 12-week period of study interventions, subjects will return to the clinic three times per week (ideally on Monday, Wednesday, and Friday). Assessments will be performed as follows:

On Day 1, Week 1 before dosing:

All women will have a pregnancy test on the day that first dose of investigational product is administered prior to the dose to confirm that the subject is not pregnant.

At each visit:

- 1. SUR
- 2. Urine methamphetamine and creatinine
- 3. Alcohol breathalyzer (if necessary, according to institutional policies)
- 4. AEs
- 5. Concomitant medications
- 6. Compliance with study interventions [investigational product dosing (by subject self report; pill counts are performed once per week) and CBT]

Once per week preferably at the first visit of each week (except at the end of Week 12):

- 1. Urine drug screen (urine specimen sent to central laboratory for analysis)
- 2. BSCS
- 3. CGI-S
- 4. CGI-O
- 5. Vital signs
- 6. Compliance with study interventions (pill count)

At Weeks 6 and 12, preferably at the first visit of the week:

- 1. Blood for RNA analysis
- 2. Blood for trough plasma bupropion levels (hold morning dose until blood sample obtained)
- 3. Blood for plasma BDNF levels

At Weeks 4 and 8, preferably at the first visit of the week, and Week 12 at the last visit of the week:

- 1. Pregnancy test
- 2. AISRS

At Weeks 2, 4, 6, 8, 10 and 12, preferably at the first visit of the week (except at the end of Week 12):

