13.6.30 Genetic Analysis

Conduct of the following analyses will be dependent upon favorable efficacy findings. Microarray technology from Affymetric will be used to perform genotyping (on DNA samples) and expression analysis (on RNA samples). The GeneChip® Mapping 500K array set will be used for genotyping and the Human Genome U-133 Plus 2.0 array will be used for expression analysis. Blood samples for genetic analysis will be collected using standard phlebotomy techniques into VacutainerTM tubes containing special preservatives for subsequent isolation of RNA and DNA. Blood for RNA isolation will be collected at approximately the same time of day for each individual for all three collection time points to control for circadian rhythm effects on expression.

Two blood samples will be collected from every individual who consented to genetics analysis for genotyping (PAXgeneTM Blood DNA). Blood samples for expression analysis will be collected into PAXgeneTM Blood RNA Tubes. All of these samples will be sent to Expression Analysis for processing. Detailed procedures for the proper collection of blood for genotyping and expression analysis and shipping to Expression Analysis are provided in the study's Operations Manual. Blood must be shipped the same day that it was collected and only should be collected on Mondays through Wednesday to assure delivery to the laboratory during the workweek.

Gene expression and SNP profile data produced at Expression Analysis will be submitted to Information Management Consultants (IMC) for data warehousing and analysis.

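### Table 1 puts the Week 12 RNA, bupropion and BDNF draws at the last visit, which on the usual visit grid falls in the dose taper; section 13.3 prefers the first visit

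*Protocol*

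**What the plan says.** All references are to the protocol.

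- **Table 1.** The Week 12 cells for RNA blood, plasma bupropion and plasma BDNF carry footnote l: "These assessments are performed at the last visit of Week 12 or at earlier termination".
- **Section 13.3.** The same three draws are scheduled "At Weeks 6 and 12, preferably at the first visit of the week", and the bupropion sample is described as a trough with the morning dose held. Other Week 12 items are expressly moved. The pregnancy test and AISRS are listed for Weeks 4 and 8 "and Week 12 at the last visit of the week", and the weekly items and the HAM-D carry an exception for the end of Week 12. The three blood draws carry none.
- **Sections 13.4 and 12.5.** Neither the termination list nor the completion interview includes the three draws.
- **Section 11.1 and the synopsis.** The taper is placed "During the last 3 days of study interventions during Week 12 or before termination"; the synopsis agrees ("dose taper will be performed the last 3 days of the 12 weeks, to 150 mg per day").
- **Section 13.6.30.** Blood for genetic analysis, which includes RNA, is shipped the day it is drawn and "only should be collected on Mondays through Wednesday to assure delivery to the laboratory during the workweek".
- **Sections 13.6.6 and 13.6.9.** Plasma for BDNF and bupropion is frozen and shipped in batches.

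**The concern.** A site working from Table 1 and a site working from section 13.3 can draw the Week 12 samples on different days, each believing that it complies. Near the end of Week 12 this matters, because the dose is being reduced. A bupropion level taken during the taper is not the full-dose trough that sections 13.3 and 13.6.9 aim for. A lower value could be read as fast clearance or poor compliance when it only reflects the visit chosen.

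The levels are to be correlated with CYP2B6 haplotype and with treatment success (section 15.2.2, on plasma levels). Bupropion blood level is also a factor in the secondary analysis of the primary outcome (section 15.4.1), and is related to genetic markers and safety in section 15.4.4.

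Footnote l's early-termination clause adds a further problem. Section 11.1 asks participants to taper before stopping, and section 15.2.1 scores those who drop out before the last two weeks as failures. If such samples were pooled with the Week 12 levels as troughs, low levels and failure could go together because of the taper.

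**Working it through.** **1. Calendar.** Inputs:
- Week 12 is days 78–84. Section 15.2.2, outcome B, defines weeks as 7-day periods from the first dose; applying that to visit weeks is an assumption.
- The taper covers the last three days, 82–84 (section 11.1).
- Visits are "ideally on Monday, Wednesday, and Friday" (section 13.3).
- Day 1 is taken in turn as each weekday from Monday to Friday.

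| Day 1 | First Week 12 visit | Last Week 12 visit | Last visit in taper? | Last visit Mon–Wed? |
|---|---|---|---|---|
| Mon | day 78, Mon | day 82, Fri | yes | no |
| Tue | day 79, Wed | day 84, Mon | yes | yes |
| Wed | day 78, Wed | day 83, Mon | yes | yes |
| Thu | day 79, Fri | day 84, Wed | yes | yes |
| Fri | day 78, Fri | day 83, Wed | yes | yes |

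The last visit is a taper day in 5 of 5 cases and falls outside Monday–Wednesday in 1 of 5. The first visit is never in the taper, but it is a Friday for Thursday and Friday starts.

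**2. Effect on the pre-dose bupropion level.** Inputs:
- Section 4.2.3: "The half-life of bupropion is approximately 21 hours after chronic dosing".
- Doses at 09:00 and 17:00, the midpoints of the windows in section 10.3.
- Sample at 09:00 before the dose. The single taper tablet is tried at either time.
- Linear, one-compartment superposition, in units of one tablet's initial contribution.

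Fraction remaining after 24 h: r = 2^(−24/21) = 0.453. After 16 h: 2^(−16/21) = 0.590.

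Full-dose trough: (0.590 + 0.453)/(1 − 0.453) = 1.906.

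- **Day 82:** all earlier doses were full, so the ratio is 1.00.
- **Day 83:** one tablet was taken on day 82.
  - Morning tablet: 0.453 × 1.906 + 0.453 = 1.316; ratio 0.69.
  - Evening tablet: 0.453 × 1.906 + 0.590 = 1.453; ratio 0.76.
- **Day 84:** one tablet was taken on each of days 82 and 83.
  - Morning: 0.453 × 1.316 + 0.453 = 1.049; ratio 0.55.
  - Evening: 0.453 × 1.453 + 0.590 = 1.248; ratio 0.65.

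The reduction is therefore 0% on day 82, about 24–31% on day 83 and about 35–45% on day 84. With the half-life varied by the 20% coefficient of variation in section 4.2.3 (16.8–25.2 h), the ratios are 0.63–0.79 on day 83 and 0.50–0.67 on day 84.

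**3. Combining the two.** On this grid the only weekday breach is the Monday starter's Friday (day 82), when the pre-dose bupropion level is still that of full dosing. The participants with a lowered level (days 83 and 84) are on permitted weekdays. The two problems fall on different participants.

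**The case against.** Several points on the other side stand.

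- **Section 13.3 states a preference.** A reader might infer two mandatory rules in collision. It says only that the first visit is preferred, so a later draw also complies with it. The conflict remains, because footnote l is unqualified and points to the other end of the week.
- **It may be clerical.** That sections 13.4 and 12.5 omit these draws suggests that footnote l was applied too widely. That makes correction easy, but sites may work from the table.
- **The weekday rule is narrow.** A reader might infer that all three draws can miss the permitted shipping days. The rule covers genetic blood only; plasma is frozen and batched.
- **The drop should not be overstated.** A pre-dose draw within Week 12 comes at most about 48 hours after the first taper morning, so 72 hours on the taper cannot be reached. Section 4.2.3 also describes biphasic kinetics, so the single half-life is an illustration.
- **Other consequences are not supported.** Section 15.4.4 compares each later expression profile with the pre-treatment one and names no Week 6 to Week 12 contrast. Nothing in the protocol shows that a short taper shifts BDNF or RNA. Section 15.4.1 does not say which week's blood level it uses, and the scheduled taper does not touch the Week 6 sample.
- **Timing data exist.** Section 13.6.9 records draw time and last-dose time, and section 10.6 records self-reported product use at each visit. Mistimed samples can be identified, but they cannot be retaken as full-dose troughs.

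**Conclusion.** The contradiction is in the current text. On the protocol's preferred visit days, following Table 1 puts every scheduled Week 12 draw on a taper day. For bupropion the visit choice alone lowers the pre-dose level by nothing for Monday starters, about 24–31% on day 83 and about 35–45% on day 84, in fully compliant participants. That confounds the Week 12 level with the taper in the CYP2B6, treatment-success and blood-level analyses. The RNA weekday breach is a separate, smaller problem confined to Monday starts.

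The figures rest on study weeks counted from first dose, exact Monday–Wednesday–Friday visits, the assumed clock times and a single 21-hour half-life. The distribution of start weekdays is not given, so no average effect can be stated. The analyses affected are secondary or exploratory, and the genetic work depends on favorable efficacy findings. The primary test and sample size do not use these samples.

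**What to change.** 1. Reconcile Table 1 with sections 13.3 and 13.4: remove footnote l from the RNA, bupropion and BDNF rows and state that the Week 12 draw is taken at the first Week 12 visit, before the taper.
2. For RNA, allow a Monday-to-Wednesday visit in or adjacent to Week 12 and before the taper. A first-visit rule alone gives a Friday for Thursday and Friday starts. A Friday starter has a Monday visit on day 81. A Thursday starter has no Monday-to-Wednesday visit in Week 12 before the taper, and would use the Wednesday on day 77.
3. Use the dose and draw times already collected (sections 13.6.9 and 10.6) to flag any sample taken during or after the taper, including at early termination, and do not treat it as a full-dose trough.

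This changes the timing of research samples only and leaves the taper as it is. It costs a table correction and a note to sites, with no added tubes. Thursday and Friday starters may need RNA drawn at a different visit from the plasma unless all three draws are moved together.

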13.2 BASELINE ASSESSMENTS

Baseline assessments to be completed over a 14-day consecutive period prior to randomization include the following:

- 1. The following will be obtained at each baseline visit (visits should be scheduled to occur three times a week for two weeks):
 - a. Alcohol breathalyzer test (if necessary, according to institutional policies)
 - b. AEs
 - c. Concomitant medications
 - d. Urine drug screen using an onsite testing device. Subjects must provide at least 4 urine specimens in a consecutive 14-day period with at least 2 of the specimens being collected during each of the two weeks. Ideally, 3 of the specimens will be obtained in one week and 3 in the next week. Also, no more than two specimens can be collected on consecutive days.
 - e. Urine methamphetamine plus creatinine measurements. Note: Methamphetamine assay will be performed only for the urine samples collected for the subjects who are randomized on the study.
 - f. CBT compliance (two 60-minute sessions weekly, to be checked every visit and verified with the CBT attendance log)
- 2. The following will be obtained weekly for two weeks:
 - a. BSCS
 - b. CGI-S
 - c. CGI-O
 - d. HAM-D
 - e. Urine drug screen (all urine specimens will be sent to a central laboratory for analysis). This is only for subjects who are randomized on the study.
- 3. Daily report of methamphetamine, marijuana, nicotine, alcohol, opiates, and cocaine use will be recorded at each visit on a SUR CRF.
- 4. The following will be obtained once during baseline:
 - a. ASI-Lite (If the ASI-Lite taken during screening is not during the baseline period, this assessment must be repeated during baseline. The reason for taking this during screening is to try to capture this data for all subjects for the genetics analysis, even if not enrolled in the study).
 - b. AISRS
 - c. HRBS
- 5. The Eligibility Checklist will be reviewed one final time at the end of the baseline period before randomization to ensure eligibility to participate in the study.

13.3 ASSESSMENTS DURING THE INTERVENTION PHASE

Over the 12-week period of study interventions, subjects will return to the clinic three times per week (ideally on Monday, Wednesday, and Friday). Assessments will be performed as follows:

On Day 1, Week 1 before dosing:

All women will have a pregnancy test on the day that first dose of investigational product is administered prior to the dose to confirm that the subject is not pregnant.

At each visit:

- 1. SUR
- 2. Urine methamphetamine and creatinine
- 3. Alcohol breathalyzer (if necessary, according to institutional policies)
- 4. AEs
- 5. Concomitant medications
- 6. Compliance with study interventions [investigational product dosing (by subject self report; pill counts are performed once per week) and CBT]

Once per week preferably at the first visit of each week (except at the end of Week 12):

- 1. Urine drug screen (urine specimen sent to central laboratory for analysis)
- 2. BSCS
- 3. CGI-S
- 4. CGI-O
- 5. Vital signs
- 6. Compliance with study interventions (pill count)

At Weeks 6 and 12, preferably at the first visit of the week:

- 1. Blood for RNA analysis
- 2. Blood for trough plasma bupropion levels (hold morning dose until blood sample obtained)
- 3. Blood for plasma BDNF levels

At Weeks 4 and 8, preferably at the first visit of the week, and Week 12 at the last visit of the week:

- 1. Pregnancy test
- 2. AISRS

At Weeks 2, 4, 6, 8, 10 and 12, preferably at the first visit of the week (except at the end of Week 12):

1. HAM-D

NOTE: Blood chemistries and hematologies will be performed during the intervention phase of the study if considered necessary by a study principal investigator.

13.4 ASSESSMENTS AT TERMINATION

At the end of Study Week 12 or if the subject discontinues prematurely, regardless of the reason (request that the subject return for final assessments), the following assessments will be performed:

1. If the subject discontinued prematurely, determine the reason for termination and complete the End of Trial form.

- 2. Physical exam
- 3. Vital signs
- 4. SUR
- 5. Urine methamphetamine and creatinine
- 6. Alcohol breathalyzer (if necessary, according to institutional policies)
- 7. AEs
- 8. Urine drug screen (urine specimen sent to central laboratory for analysis but only if a specimen was not already collected during that week)
- 9. BSCS
- 10. CGI-S
- 11. CGI-O
- 12. Hematology
- 13. Blood chemistries
- 14. Medical Urinalysis
- 15. Pregnancy Test
- 16. ASI-Lite
- 17. HRBS
- 18. HAM-D
- 19. AISRS
- 20. ECG
- 21. Concomitant medications
- 22. Compliance with study interventions (investigational product dosing and CBT)

